	APPENDIX 3 INDEX OF SEVERITY FOR OSTEOARTHRITIS OF THE HIP BY LEQUESNE ET AL.	

1. LIST OF ABBREVIATIONS

ADE	Adverse Device Effect
AE	Adverse Event
CA	Competent Authority
DMP	Data Management Plan
EC	Ethics Committee
FDA	Food and Drug Administration
HA	Hyaluronan / Sodium Hyaluronate / Hyaluronic Acid
HIPAA	Health Insurance Portability and Accountability Act
IA	Intra-articular
ICF	Informed Consent Form
ICH	International Conference on Harmonization
IFU	Instructions for Use
ISO	International Organization for Standardization
ITT	Intent to Treat
MedDRA	Medical Dictionary for Regulatory Activities
OA	Osteoarthritis
PGA	Patient Global Assessment
PI	Principal Investigator
PP	Per Protocol
SADE	Serious Adverse Device Effect
SAE	Serious Adverse Event
SAP	Statistical Analysis Plan
SOP	Standard Operating Procedure
UADE	Unanticipated Adverse Device Event
USADE	Unanticipated Serious Adverse Device Effect

2. STUDY SYNOPSIS

Title	A Prospective Study of a Single Injection Cross-linked Sodium Hyaluronate combined with Triamcinolone Hexacetonide (CINGAL®) to Provide Symptomatic Relief of Osteoarthritis of Hip Joint
Study Objective	To obtain clinical data to support an expanded indication for a single injection of Cingal® used for the symptomatic relief of osteoarthritis in the hip joint.
Investigational Product	CINGAL®: A chemically cross-linked sodium hyaluronate combined with Triamcinolone Hexacetonide supplied as a 4-mL unit dose in a 5-mL glass syringe.
Mode of Delivery	Cingal will be injected into the intraarticular (IA) space of the index hip using an 18-21-gauge needle. Intra-articular injection of the index hip joint may be conducted under fluoroscopic or ultrasound guidance as required by standard of care treatment.
Study Design	Prospective, multi-center, open label expanded indication clinical trial.
Phase	Phase III
Sample Size	25 subjects will be enrolled and treated.
Study Duration	The entire study duration from first subject in to last subject out will be approximately one and half years. The enrollment phase will be approximately 12 months with a follow-up phase of 6 months. Visits will be scheduled at screening, baseline, 1 month, 3 months and 6 months post treatment. First patient in is expected Nov - Dec 2020.
Inclusion Criteria	
Screening Inclusion Criteria
 
 1. Age 18 years or older 2. Body Mass Index (BMI) $\leq 35 \text{ kg/m}^2$ 3. Diagnosis of symptomatic osteoarthritic joint in the index hip (Kellgren-Lawrence grade I to III) to be treated with Cingal injection. 4. Failed conservative treatment for joint osteoarthritis. 5. NRS pain on walking ≥ 4 and ≤ 9 in index hip. 6. Subject must be willing to abstain from other treatments of the index hip for the duration of the study. 7. Subject is willing to discontinue all analgesics including NSAIDs, except acetaminophen/paracetamol, at least seven days before the treatment injection and through the completion of the study. 8. Subject is willing to use only acetaminophen/paracetamol (up to a maximum of 4.0 grams per day per the package insert) for the treatment of joint pain for the duration of the study. At least forty-eight hours prior to the Baseline Visit and each follow-up visit, the subject is willing to discontinue use of acetaminophen/paracetamol. 9. Subject is willing to maintain a stable dose of oral glucosamine and/or chondroitin sulfate products throughout the study, if taken prior to signing the informed consent form (ICF). 10. Able and willing to provide signed informed consent. 
Screening Exclusion Criteria
 
 1. History of hypersensitivity to any of the ingredients in the hyaluronan or corticosteroids 2. Infection or skin disease in the area of the injection site or hip joint 3. NRS pain on walking > 3 in the contralateral hip 4. NRS pain on walking > 3 in the ipsilateral knee or ankle 5. Subject received an injection of Hyaluronic Acid (HA) and/or steroid in either joint within 6 months of signing the informed consent form (ICF). A subject will be excluded if they are planning to receive an HA or steroid injection (other than the study injection) in either joint during the course of this study. 6. Known inflammatory or autoimmune disorders (including rheumatoid arthritis, gout), or other pre-existing medical conditions that, in the opinion of the investigator, could impact treatment of the hip joint or affect the ability of the subject to accurately complete the study questionnaires and comply with the study requirements. 7. Subject is taking medications at the time of signing the ICF which could interfere with the treatment procedure, healing and/or assessments. This includes but is

	
not limited to oral or injectable anticoagulant treatments, anti-aggregant platelet treatment, chronic opioid analgesics. Low dose aspirin used for cardiovascular protection is allowed if a stable regimen is maintained for the duration of the study.
 
8. Subjects who had an oral, intramuscular, intravenous, rectal suppository or topical (excluded in hip joint only) corticosteroid prior 30 days of signing the ICF are excluded. Topical corticosteroid use at any site other than the hip joint is allowed.
 
9. Significant trauma to the index hip within 26 weeks of screening
 
10. Chronic use of narcotics or cannabis.
 
11. Ligament instability or tear in hip joint.
 
12. Diagnosis of fibromyalgia
 
13. Diagnosis of osteonecrosis in hip joint
 
14. Subject has significant varus or valgus deformity greater than 10 degrees in either knee.
 
15. Subject requires consistent use of an assistive device (e.g. wheelchair, walker, etc.) Occasional use of a cane is acceptable.
 
16. Uncontrolled diabetes with HbA1c of >7%.
 
17. Subject is a woman who is pregnant or breastfeeding at the Screening Visit or a woman of child bearing potential who refuses to use effective contraception during the course of the study.
 
18. Subject is receiving or in litigation for worker's compensation.
 
19. Otherwise determined by the investigator to be medically unsuitable for participation in this study.
 
Baseline Inclusion Criteria
 
1. NRS pain on walking ≥ 4 and ≤ 9 in index hip
 
Baseline Exclusion Criteria
 
1. Subject has a decrease of ≥ 2 in the NRS pain on walking from Screening to Baseline in the index hip.
 
2. Subject has a contraindication to continue with the study treatment injection based on the visual appearance of the synovial fluid aspirate.

Criteria for Evaluation	
Primary Endpoint:
 
 Reduction of index hip Numerical Rating Scale (NRS) pain on walking from baseline to 6 Months post injection. 
Secondary Endpoints:
 
 Improvement in Lequesne Hip index from baseline to 6 months post injection. Improvement in Patient Global Assessment (PGA) from baseline to 6 months post injection. OMERACT-OARSI responder rate in index hip at 6 months post injection. Time to treatment failure Reduction in Medication usage from baseline to 6 months post injection. 
Exploratory Endpoints
 
Any comparisons across timepoints (baseline to 6 months) not described in the primary or secondary endpoints including but not limited to:
 
 Demographics Medical History

	
 • History of joint osteoarthritis • Rescue Medication Use • Treatment Failure • Injection procedure • Concomitant medications • Non-drug therapy 
Safety Endpoint:
 
The incidence, severity, and relationship to treatment of all Adverse Events (AE) will be collected from the first treatment injection to the 6 month assessment.

Statistical Analysis	
The primary analysis on the endpoints will be performed on the ITT (Intent to Treat) populations. All Primary and Secondary endpoints will be analyzed using the ITT population.
 
A secondary analysis will be conducted on the Per Protocol (PP) population. Since the primary endpoint is at 6 months this is all subjects who complete the 6 month assessment and do not have a major deviation in the conduct of the protocol. For all other visits, this is defined as the subjects who complete those visits according to the protocol.
 
All safety analyses will be conducted on all subjects who undergo treatment of Cingal in the hip joint.

Sites	Up to 10 clinical sites in EU
Sponsor	
Anika Therapeutics, Inc. [name], United States of America
 
Phone: + 1 [contact] Fax: + 1 [contact]

3. INTRODUCTION

Osteoarthritis (OA) is the most prevalent joint disorder worldwide and is associated with significant pain and disability [1]. It is a progressive disease that can affect any joint but most often involves the weight bearing joints such as the knee. The European Project on Osteoarthritis reported on prevalence rates for knee OA in Europe and the United Kingdom (UK). For subjects aged 65-74 years, the rate of knee OA based on clinical judgment was 36.7% in Italy and 18.6 % in the UK. For subjects aged 75 years or older the rate, based on clinical judgment was 50.8% in Italy. In the Netherlands, the self-reported rate of knee OA in subjects 65-74 years was 23.6% and for subjects 75 years or older was 31.4% [2]. Because of the high prevalence of knee OA, this disease ranked as either the top or second leading cause of disability [3]. In particular, this disease accounted for more dependence on others in climbing stairs, housekeeping and walking a mile than any other disease after adjustment for age, sex and comorbidity [3].

Osteoarthritis is defined as a “heterogenous group of conditions that leads to joint symptoms and signs which are associated with defective integrity of articular cartilage in addition to related changes in the underlying bone and at the joint margins” [4]. OA is characterized by a decreased concentration of HA in synovial fluid and a slow degradation of cartilage over years [5, 6]. The decreased concentration of HA in the synovial fluid of an osteoarthritic joint is probably caused by dilution from exudation, a decreased production of hyaluronans, and increased degradation [6]. Accordingly, the average molecular weight is diminished resulting in a loss of the viscoelastic properties of the synovial fluid for which HA is responsible [5].

Corticosteroids have long been used to alleviate pain and inflammation by injecting into the intra-articular space. Commonly used corticosteroids have been triamcinolone acetonide (TA) and triamcinolone hexacetonide (TH) which have been reviewed in the literature and found to be safe and effective for short term relief of the symptoms of osteoarthritis [7]. Standard dosing for intra-articular injections to the knee for triamcinolone hexacetonide (TH) have been reported as a 1 ml injection at a concentration of 20 mg/ml which will be the proposed dose for the active control in this trial [7].

Viscosupplements are believed to restore the concentration of hyaluronans in synovial fluid, elevate the viscosity and improve the lubricating and cushioning properties of the synovial fluid to a healthier state to alleviate pain in OA [6]. HA in synovial fluid binds to chondrocytes, supporting a role for HA in healthy cartilage [5]. HA has been studied as a substance capable of restoring the normal properties of synovial fluid and cartilage, thereby reducing pain and stiffness in the osteoarthritic joints. Exogenously administered HA immediately restores the synovial fluid's viscoelastic (or rheologic) properties [6].

Bellamy et al (2006) conducted a systematic analysis of 76 single and double-blinded studies and concluded that viscosupplements are an effective treatment for OA of the knee with beneficial effects on pain, function and Patient Global Assessment from a 5 to 13 week post injection period showing a percent improvement from baseline of 28% to 54% for pain and 9% to 32% for function [8].

Because data show a delayed treatment effect of HA, Anika Therapeutics created a product, Cingal®, that could provide quicker pain relief for subjects suffering from osteoarthritis while still providing the established pain relief of an HA product. Anika chose to add a corticosteroid, triamcinolone hexacetonide (TH), that was approved in the U.S. and Europe for intra-articular use in osteoarthritis and was labeled for frequency of injection every 3-4 weeks, to a cross-linked HA product which provides pain relief of up to 26 weeks after a single injection.

Cingal® is a sterile, biocompatible, non-pyrogenic, viscoelastic, uniform white/off white opaque solution composed of molecules of HA and triamcinolone hexacetonide (TH). Cingal® is intended to treat the pain of osteoarthritis (OA) of the knee in patients who have failed to respond to conservative non-pharmacological therapy and to simple analgesics, e.g., acetaminophen. Cingal® functions as a viscoelastic supplement or a replacement for synovial fluid in human joints with short term pain relief is provided by triamcinolone hexacetonide.

Cingal® has been studied in two Phase III trials, Cingal 13-01 and Cingal 16-02, and several follow-on studies, Cingal 13-02 and Cingal 17-02 [26-29]. Cingal® studies generated a safety data base of 642 subjects treated intra-articularly with a Cingal® injection, including 94 subjects retreated with a second injection.

Hyaluronic Acid injections in non-knee synovial joints has been reported to show benefits in pain reduction and improvement in joint function. Patients with hip osteoarthritis had significantly improved Lequesne's function and reduced VAS pain at 3 and 6 months after injection (Migliore et al. *Arthritis Research & Therapy* 2009 Vol 11 No 6). A study on the use of intra-articular HA in the treatment of symptomatic osteoarthritis of the shoulder showed an improvement in VAS score of 24 points from baseline to 6-months (Silverstein et al. *Am J of Sports Medicine*, 2007, Vol 35, No. 6). The effect of a single injection of HA on patients with symptomatic ankle (talo-crural) osteoarthritis show an improvement in VAS score of 44.5 points from baseline to 3 months (Witteveen A.G.H. et al. *J Foot and Ankle Surgery* 2008 Vol 14 p145-152).

The goal of this study is to demonstrate the clinical improvement and safety in patients treated with Cingal for hip osteoarthritis. Specifically, this study will provide confirmation to the safety and performance of Cingal at relieving hip joint pain to 6 months post-treatment.

4. BENEFITS / RISKS

4.1 Benefits

Intra-articular injections of Cingal and other hyaluronic acid viscosupplements have shown significant clinical benefits for knee osteoarthritis patients. It is anticipated that such benefits may result from the use of Cingal to treat hip OA pain.

4.2 Risks

Any intra-articular injection poses potential risks. However, subjects should incur no additional risks compared to injections of other frequently injected products, such as corticosteroids or diagnostic contrast agents.

Effects associated with Hyaluronic Acid

Hyaluronic acid is a naturally occurring component of the tissues of the body. Cingal is thoroughly tested to determine that each batch conforms to the product quality attributes. Mild to moderate episodes of transient swelling and discomfort have occasionally been observed following intra-articular injection of hyaluronic acid preparations. A risk of infection is possible with the procedure of injecting substances into joints.

Effects associated with Triamcinolone Hexacetonide

For assessment of adverse reactions (ADRs) following terms regarding frequency are used:

very common ($\geq 1/10$)

common ($\geq 1/100$ to $< 1/10$)

uncommon ($\geq 1/1,000$ to $< 1/100$)

rare ($\geq 1/10,000$ to $1/1,000$)

very rare ($< 1/10,000$)

not known (cannot be estimated from the available data)

Adverse effects depend on the dose and the duration of treatment. Systemic adverse effects are rare but may occur as a result of repeated periarticular injection. As with other intraarticular steroid treatments, transient adrenocortical suppression has been observed during the first week after injection. This effect is enhanced if corticotropin or oral steroids are used concomitantly.

Immune system disorders

Very rare: anaphylaxis-type reactions

Not known exacerbation or masking of infections

Endocrine disorders

Not known menstrual irregularities, amenorrhoea and postmenopausal vaginal bleeding; hirsutism; development of a cushingoid state; secondary adrenocortical and pituitary unresponsiveness, particularly during periods of stress (e.g. trauma, surgery or illness); decreased carbohydrate tolerance; manifestation of latent diabetes mellitus

Psychiatric disorders

Not known insomnia; exacerbation of existing psychiatric symptoms; depression (sometimes severe); euphoria; mood swings; psychotic symptoms

Nervous system disorders

Rare: vertigo

Not known: increased intracranial pressure with papilloedema (pseudotumor cerebri) usually after treatment; headache

Eye disorders

Not known: posterior subcapsular cataracts; increased intraocular pressure; glaucoma

Cardiac disorders

Not known: cardiac failure; arrhythmias

Vascular disorders

Very rare: thromboembolism

Not known: hypertension

Gastrointestinal disorders

Not known peptic ulcers with possibility of subsequent perforation and haemorrhage; pancreatitis

Skin and subcutaneous tissue disorders

Very rare: hyperpigmentation or hypopigmentation

Not known: impaired wound healing; thin and fragile skin; petechiae and ecchymoses; facial erythema; increased sweating; purpura; striae; acneiform eruptions; hives; rash

Musculoskeletal and connective tissue disorders

Very rare: calcinosis; tendon rupture

Not known: loss of muscle mass; osteoporosis; aseptic necrosis of the heads of the humerus and femur; spontaneous fractures; Charcotlike arthropathy

Renal and urinary disorders

Not known: negative nitrogen balance owing to protein catabolism

General disorders and administration site conditions

Common: Local reactions include sterile abscesses, post-injection erythema, pain, swelling and necrosis at the injection site.

Rare: Excess dosage or too-frequent administration of injections into the same site may cause local subcutaneous atrophy, which, due to the properties of the drug will only return to normal after several months.

Adverse events associated with single intra-articular knee injections of Cingal can be found in the Cingal Investigator's Brochure. These events are expected to be similar for hip injections. In the clinical trial for Cingal in knee OA, adverse events that were related to the injection treatment were:

- injection site pain/swelling
- joint stiffness / swelling / effusion
- arthralgia,
- pain in extremity
- synovitis
- contusion
- subcutaneous nodule
- Baker's cyst

Adverse events not related to the knee for Cingal were:

- headache
- pain in extremity
- upper respiratory tract infection
- back pain

Other risks associated with intra-articular hip injections, regardless of treatment, include:

- temporary injection site pain, swelling or tenderness
- temporary stiffness of the hip
- malfunction of the syringe and/or needle

In rare instances, side effects could include:

- an allergic reaction to the fluoroscopic imaging contrast agent. Symptoms could include redness or inflammation at the injection site or inside the hip joint, hives or itching.
- an allergic reaction to the local anesthetic (lidocaine). Symptoms could include redness or inflammation at the injection site or inside the hip joint, hives or itching.
- injection site infection
- neurovascular, cartilage, or bone damage resulting from the injection itself

Finally, there is a low risk associated with radiation from the X-ray evaluation required for inclusion in the study. There is also a low risk from the radiation during fluoroscopy-guided injections

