7.3.9.6 Subject Diary

Subjects will receive diary for to record rescue medications and concomitant medications.

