7.5 Follow-Up Visits

All study subjects will have follow-up visits at 1, 3 and 6 Months after Baseline to evaluate the joint pain score and to assess adverse events.

The subject should be contacted at least 48 hours prior to their scheduled assessments to be reminded of the required assessment (and applicable wash out period) and to schedule the date and time of contact. At least three documented attempts will be made to contact the subject in order to accomplish maximum subject compliance with the follow-up schedule.

The following tests will be performed at the follow-up visits at 1, 3 and 6 months.

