8. SAFETY PROCESSES

Safety of the subjects participating in this clinical investigation will be monitored throughout the clinical investigation using the Adverse Event (AE) reporting process in the EDC system, to identify real and potential safety issues.

Adverse events will be reported according to the ISO 14155:2011, while recognizing and following the requirements including reporting timelines specified in other specific laws, regulations, directives, standards and/or guidelines as appropriate and as required by the countries in which the study is conducted.

All AEs that occur during or after injection will be recorded. Worsening of a condition that existed prior to the study injection should be recorded as an AE. At each assessment during the trial, AEs that have occurred since the previous assessment must be recorded. All subjects will be questioned and evaluated for AEs or complications associated with the procedure. Complications of the injection include, but are not necessarily limited to: pain, swelling, erythema, bleeding and/or infection at the injection site. The Investigator will determine the severity and relationship of each event, as defined above.

AEs observed during the course of this study, regardless of severity or relationship to the device and/or the procedure will be recorded on the CRF. Each reported complication/AE will also include the duration, action taken to address the AE, and the resolution status (e.g. ongoing, resolved). These subjects will continue to be evaluated for safety at all scheduled follow-up points.

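### Expected early local reactions to the injection are first asked about at Month 1, and the diary already in use has no place to record them

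*Protocol*

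**What the plan says.** **What is expected.** Section 4.2 makes three separate statements about local effects.
- For the steroid component: "Common: Local reactions include sterile abscesses, post-injection erythema, pain, swelling and necrosis at the injection site". The frequency scale in the same section defines common as at least 1 in 100 and under 1 in 10.
- For the hyaluronic acid component: "Mild to moderate episodes of transient swelling and discomfort have occasionally been observed following intra-articular injection of hyaluronic acid preparations".
- For any hip injection, with no frequency given: "temporary injection site pain, swelling or tenderness", and temporary stiffness.

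**What is measured.** The synopsis gives one endpoint for safety: "The incidence, severity, and relationship to treatment of all Adverse Events (AE) will be collected from the first treatment injection to the 6 month assessment". Section 6.4 repeats it in substance.

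**When subjects are asked.** Section 7.4 requires an AE evaluation before the subject leaves the clinic. Section 7.5 then says "All study subjects will have follow-up visits at 1, 3 and 6 Months after Baseline", and the schedule in Section 7.1 places AE assessment at Baseline and Months 1, 3 and 6. Section 8 sets the look-back: "At each assessment during the trial, AEs that have occurred since the previous assessment must be recorded".

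**What the diary holds.** Section 7.3.9.6: "Subjects will receive diary for to record rescue medications and concomitant medications". The schedule has it dispensed at Baseline and collected and reviewed at Month 1.

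**Other routes between visits.** Section 7.4 asks subjects to tell the study team about unexpected symptoms. Section 7.3.9.3 makes the indication for a new medication an AE unless the condition already existed.

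**The concern.** The reactions most to be expected from an injection can appear and settle within days. Under this schedule nobody asks about them until about four weeks later, which is also when a resolved reaction would be graded for severity and for its relationship to device and procedure (Section 8.3). A mild reaction that has gone by then may be forgotten, or remembered as milder than it was.

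The incidence, severity and relationship of AEs make up the whole safety endpoint, and Section 3 states that the study is to confirm safety in the hip. There is no control arm and only 25 subjects are planned, so each subject with a missed reaction moves the incidence by 1/25 = 4 percentage points. This is a matter of data collection fixed by the protocol. No later analysis can recover symptoms that were never written down.

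**Working it through.** **Step 1: the gap.** Take a month as 30 days. Month 1 falls 27 to 33 days after injection under the ±3-day window in Section 7.1, and 23 to 37 days after it under the ±7-day heading of Section 7.6. No AE questioning is scheduled in between. The contact in Section 7.5, at least 48 hours before a visit, is described as a reminder of the visit and washout, and for scheduling.

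**Step 2: do the other routes cover expected local reactions?**

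| Route | What triggers it | Expected mild local reaction covered? |
|---|---|---|
| Self-report (Section 7.4) | A symptom the subject regards as unexpected | Not by its wording; staff have just discussed with the subject what to expect |
| New-medication indication (Section 7.3.9.3) | A medication started after treatment | Only if something new is taken |
| Diary (Section 7.3.9.6) | Use of rescue or concomitant medication | Only indirectly |

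The medication routes are weakest for injection-site pain. Section 7.4 allows acetaminophen/paracetamol for it, and Section 7.3.9.2 makes the same drug the rescue medication for the index hip. A subject already using it starts nothing new, and a pill count cannot by itself separate injection pain from osteoarthritis pain. Cold therapy, also allowed in Section 7.4, is not a medication.

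**Step 3: the recording rule.** Section 7.4 says that unexpected post-treatment signs and symptoms should be recorded as AEs. Section 8 says that all AEs during or after injection will be recorded, and names pain, swelling and erythema among the complications. A site that follows Section 7.4 literally could leave out an expected reaction that Section 8 requires.

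**Step 4: illustration of size.** The protocol gives no figure for the share of reactions captured, so there is none to reproduce. Inputs: n = 25 (synopsis); true rate p from 1% to just under 10% (the common band of Section 4.2, evaluated at 10% for the upper end); capture c = 1 or 0.5. The value 0.5 is an assumption.

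Expected recorded cases = 25 × p × c. Chance of recording at least one = 1 − (1 − p × c)^25.

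| p | c | Expected cases | Chance of at least one |
|---|---|---|---|
| 1% | 1 | 0.25 | 1 − 0.99^25 = 22% |
| 1% | 0.5 | 0.125 | 1 − 0.995^25 = 12% |
| 10% | 1 | 2.5 | 1 − 0.90^25 = 93% |
| 10% | 0.5 | 1.25 | 1 − 0.95^25 = 72% |

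At the upper end with half captured, the chance of recording none is 0.95^25 = 28%; with full capture it is 7%. The band describes the steroid component alone. The protocol gives no rate for all local reactions to the combined product in the hip.

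**The case against.** The strongest reply is that the visit schedule does not contradict itself on when AEs are assessed, and that how intensively to solicit reactions is a design choice. Section 8 requires every subject to be questioned about complications. Daily pill tracking leaves a trace that may prompt a question at Month 1, serious events reach the sponsor within 24 hours of knowledge, and a sterile abscess or necrosis is unlikely to be forgotten. All of this stands. It confines the point to mild or moderate expected reactions that resolve before Month 1, which are only part of an endpoint covering all AEs over six months.

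Four stronger readings are tempting, and the protocol does not support them.
- *Early safety data rest on recall alone.* They do not: the Day 0 check, self-report and the medication routes exist. The gap is what these leave uncovered.
- *The protocol calls local reactions both common and transient.* It does not. Common is said of the steroid reactions, including abscess and necrosis; transient is said of hyaluronic acid effects seen occasionally; temporary is said of hip injections in general.
- *Under-counting is established and its size known.* The direction is plausible, but no document gives a capture rate. A true rate such as 20% would also lie outside the band that Section 4.2 assigns to the steroid reactions.
- *The transient adrenocortical suppression in the first week (Section 4.2) would be caught by asking about symptoms.* Lines for pain, swelling and redness are not designed to detect it, so it lends no support here.

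**Conclusion.** The point holds in a limited form. Expected mild local reactions in the days after injection have no reliable route into the AE record before Month 1, and their incidence and severity are likely to be under-recorded. The extent cannot be estimated from the protocol. Within the common band, and assuming half are captured, the loss is about 0.1 to 1.25 expected cases among 25 subjects. That rests on an assumed capture rate and on a frequency band for one component only.

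The firmest textual element is the mismatch between Section 7.4 and Section 8 over whether expected reactions are recorded as AEs. Nothing here touches the primary endpoint or the sample size. It is worth correcting because the correction is cheap, not because the trial fails without it.

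**What to change.** 1. Add to the diary dispensed at Baseline a short daily line for Day 0 to Day 7 covering increase in local pain, swelling, redness and other symptoms, each with severity. Amend Section 7.3.9.6 to match.
2. Use these entries as AE source data at the Month 1 diary review, with one matching CRF form.
3. Tabulate the diary-prompted reactions apart from other AEs, so that a higher rate due to daily prompting is not mixed with events reported in the usual way.
4. Reconcile Section 7.4 with Section 8, so that one rule states whether an expected local reaction is recorded as an AE.

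**Cost.** One diary page and one CRF form, with no extra visit or staff. There is a small burden on subjects. Investigators will have more events to grade for severity and for relationship to device and procedure (Section 8.3), and the change needs an amendment submitted under Section 13.3. The recorded AE rate will probably be somewhat higher. The page would not help with reactions that begin after Day 7.
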